7. CORRELATIVE/SPECIAL STUDIES

This protocol will utilize the Translational Research Core (TRC) of the Case Comprehensive Cancer Center for the collection, processing, storage, and distribution of patient samples before and after therapy.

**Translational Research Core
ATTN [name]
University Hospitals of Cleveland
[name]
[name]
[name]
[contact]
[contact]
[name]
E-mail: [contact]**

The TRC will schedule patient sample collection in direct communication with the clinical trials research nurse. For UH patients a representative from the TRC will be present during patient sampling, wherein every sample will be given a patient identifier, and collected in the appropriate tubes or vials.

1. Pharmacokinetic studies

PK blood sampling schedule for Temozolomide (TMZ) and Methoxyamine (MX) during cycle 1 are shown in the table that follows. Depending upon the PK data from initial patients, the timing of blood draws for correlative studies may be revised for future patients. PK data during and following single one-hour MX infusion may be obtained in all subsequent cycles (cycles 2 and beyond) as necessary.

Preclinical data have not provided any evidence of significant drug interactions between TMZ and MX. However, this needs to be confirmed. TMZ is not stable in plasma, so plasma sample isolation must be carried out without delay. Plasma from one tube of whole blood will be used for both TMZ and MX determinations.

Collection Instructions for MX and TMX determinations:

1. Draw 5 ml of blood into a lithium heparinized, chilled syringe.
2. Immerse the tube in an icewater bath for 2 min.
3. Centrifuge at 1500 x g and 4 deg. C. for 5 min.
4. Transfer 1.0 ml of plasma into each of two Nunc brand cryostorage tubes.
5. To one tube, to be used for TMZ determination, add 0.1 ml of cold 1 M HCl.
6. Cap, mix, label, and store frozen at -60°C.

a) Methoxyamine determination

An LC-MS/MS method for quantitative determination of MX in human plasma was developed. In this method, MX and its stable isotope methoxyl-d₃-amine (MX-d3 as internal standard) were directly derivatized in human plasma with 4-(*N,N*-diethylamino)benzaldehyde. The derivatized MX and IS were extracted by methyl-*tert*-butyl ether, and separated isocratically on a Xterra C18 column (2.1 x 100 mm) using an aqueous mobile phase containing 45% acetonitrile and 0.4% formic acid at a flow rate of 0.200 ml/min. Quantitation of MX was carried out by multiple-reaction-monitoring (MRM) mode of positive turbo-ion-spray tandem mass spectrometry. This method has been validated according to FDA guidelines for bioanalytical method. The linear calibration range for MX was 1.25-500 ng/ml in human plasma with a correlation coefficient ≥ 0.9993 . The intra- and inter-assay precision (%CV) at three concentration levels (3.50, 45.0 and 450 ng/ml) ranged 0.9-1% and 0.8-3%, respectively. The stability studies showed that MX met the acceptable criteria under all tested conditions.

b) Temozolomide determination

Analyses will be performed in the Core Pharmacology laboratory, directed by [name].

2. DNA strand break determination by comet assay.

The comet assay is based on the ability of denatured, cleaved DNA fragments to migrate out of fixed cells under the influence of an electric field. Undamaged DNA migrates slower and remains within the confines of the nuclei when a current is applied. This assay is a simple assay but sensitively detects both single and double stranded DNA breaks, resulting from AP sites as well as other alkali labile DNA adducts in individual cells. To perform this assay, the cell suspension (1x 10⁵ /ml cold PBS) is mixed with 1% low melting point agarose at 42 °C at a ratio of 1:10 (v/v) and immediately pipetted (75 μ l) onto a CometSlide. When the agarose has set, slides are electrophoresed in both alkali and neutral solution. DNA is stained using SYBR Green and the images of comets are visualized and captured using a microscope coupled with a digital camera. DNA damage is assessed based on evaluation of the DNA “comet” tail shape and migration distance that are analyzed using Komet version 6.0 software. In previous *in vitro* studies with human lymphocytes, we have shown that DNA strand breaks are correlated with the levels of AP sites in cells treated with TMZ. A 2 hr treatment with TMZ plus MX generated higher levels of DNA strand breaks (up to 2-fold greater), compared to TMZ alone. This demonstrates that the comet assay can be used to monitor drug effects on DNA damage in clinical studies. Analyses for DNA strand breaks by comet assay will be performed in the Translational Research Core Facility lab in the Wolstein Research Building.

Collection Instructions:

1. Immediately deliver tubes to the **Translational Research Core Laboratory, [name], ([contact])** for processing and analysis by comet assay.

Cycle 1	Week 1	Day1	2	3	4	5	6
	MX	↔					
	TMZ	↓	↓	↓	↓	↓	
Correlative Studies	Pharmacokinetic Studies	0 30min 1h 2h 4h 8h	24h	48h	72h	96h	120h
	Comet assay	0 2h 4h	24h				

8. STUDY CALENDAR

Baseline evaluations are to be conducted within 2 weeks prior to start of protocol therapy. Scans and x-rays must be done \leq 4 weeks prior to the start of therapy. In the event that the patient's condition is deteriorating, laboratory evaluations should be repeated within 48 hours prior to initiation of the next cycle of therapy.

	Pre-study	C1 Wk 1	C1 Wk 2	C1 Wk 3	C1 Wk 4	Cx Wk 1 ^f	Cx Wk 2	Cw Wk 3	Cx Wk 4	Off study
Physical exam	X	X				X				X
Neurologic exam	X ^d									
MMSE	X ⁱ									
Vital signs	X	X								X
Heights	X									
Weight	X	X								X
Performance Status	X	X								X
CBC w/diff, plts	X	X	X	X	X	X ^j			X ^j	X
Serum chemistry^a	X	X	X	X	X	X				X
Serum tumor specific tumor markers^g	X									X
EKG (as indicated)	X	X								
Adverse event evaluation			X	X	X	X	X			
Tumor measurements^h	X	Tumor measurements are repeated at week 8, then every 8 weeks. Documentation (radiologic) must be provided for patients removed from study for progressive disease.								X
B-HCG	X ^b									
Pharmacokinetics^e, Lab Correlates		X ^c								

- a: Albumin, alkaline phosphatase, total bilirubin, bicarbonate, BUN, calcium, chloride, creatinine, glucose, LDH, phosphorus, potassium, total protein, SGOT [AST], SGPT [ALT], sodium.
- b: Serum pregnancy test (women of childbearing potential).
- c: See section 7.0. Pharmacokinetics will be done during week 1.
- d: All patients will be evaluated by a staff Neurologist prior to initiation of treatment and then will undergo frequent (every 4-8 hours) neurologic checks by a CRU RN during the 1-day inpatient CRU stay on cycle 1, day1.
- e: Pharmacokinetics will be obtained for the first cycle only.
- f: Subsequent cycles and associated evaluations may be conducted within +/- 2 days of the previous cycle.
- g: Tumor specific tumor markers to be obtained per physician discretion (CEA, CA 19-9, CA 125, etc) if appropriate.
- h: For cohort A, CT of the chest, abdomen and pelvis will be obtained. For cohort B, CT of the chest, abdomen and pelvis as well as MRI of the brain will be obtained if malignancy is a non-CNS primary. For primary brain tumors, CT of the chest, abdomen and pelvis not required.
- i: MMSE to be done at screening for subjects in Cohort B only. These subjects must have a score of < 15. See appendix D.
- j: CBCs to be done Days 1 and 22 for Cycles 2 and beyond, for both Cohorts.

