3.2.5 NYHA classification III or IV heart disease

3.2.6 Patients with known primary or metastatic CNS disease (cohort B) are not eligible if they have a mini mental status exam score < 15 (per Appendix D) or evidence of leptomeningeal disease.

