3.2.7 Patients with pre-existing neurologic toxicity $>$ grade 1 (as per

CTCAE, version 3.0) are not eligible for participation in cohort A. Patients screened for participation in cohort B with pre-existing neurologic toxicity > grade 2 (as per CTCAE, version 3.0) are not eligible, unless pre-existing neurotoxicity is documented in detail and patient's participation in the trial has been approved by the neuro-oncology team at participating institutions.

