4. TREATMENT PLAN

To enter eligible patients on study, investigators will register patients by contacting the study coordinator for this trial. The following information will be requested: a registration card, copy of the informed consent, and copy of the signed eligibility criteria from the study protocol. These must be submitted prior to a patient starting treatment and placed in the chart.

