4.2 Definition of Dose-Limiting Toxicity (DLT) and Criteria for Dose Escalation

DLT in a given patient is defined as any grade III non-hematologic (thought to be MX related) or IV non-hematological toxicity or any grade IV anemia, neutropenia or thrombocytopenia lasting greater than 7 days, that is felt to be related to MX or the MX + TMZ drug combination occurring during the first cycle of treatment.

MTD (maximum tolerated dose) will be defined based on the toxicities observed during the first cycle of treatment

Definition of MTD: The MTD is defined as the highest dose tested in which none or only one patient experienced DLT attributable to the study drug combination, when at least six patients were treated at that dose and are evaluable for toxicity. The MTD is one dose level below the highest dose tested in which 2 or more patients experienced DLT attributable to the study drug. At least 6 patients will be treated at the MTD.

Management and dose modifications associated with the above adverse events are outlined in Section 5.

Special consideration is given to the evaluation of neurologic toxicity given the animal toxicity data and CNS involvement of a proportion of eligible patients.

Specifically:

- all patients will be evaluated by a staff Neurologist prior to initiation of treatment
- patients will undergo frequent (every 4-8 hours) neurologic checks by a CRU RN during the 1-day inpatient CRU stay on the first day of treatment.
- Patients will be evaluated by the covering Oncology clinician during the 1-day inpatient CRU stay on cycle 1.

A neurology consult will be obtained for any observed treatment-related neurologic toxicity \geq grade 2. For patients enrolled in cohort B (patients with CNS disease) with pre-existing neurologic toxicity cleared for participation by the neuro-oncology team, a neuro-oncology or neurology consult will be obtained for any observed treatment-related worsening in neurologic toxicities.

Dose escalation will proceed within each cohort according to the following scheme. DLT is defined above.

Number of Patients with DLT at a Given Dose Level	Escalation Decision Rule
0 out of 3	Enter 3 patients at the next dose level.
≥ 2	Dose escalation will be stopped. This dose level will be declared the maximally administered dose (highest dose administered). Three (3) additional patients will be entered at the next lowest dose level if only 3 patients were treated previously at that dose.

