12. STATISTICAL CONSIDERATIONS

For cohort A, a maximum of 36 patients can theoretically participate on this study, based on 6 dose levels with a maximum of 6 patients at each dose level. However, given the fact that a 10-fold increase in MX is being tested in 6 consecutive dose escalation levels it is highly unlikely that the maximum number of patients will need to be enrolled at each level.

For cohort B, a maximum of 42 patients can theoretically participate on this study, based on 7 dose levels with a maximum of 6 patients at each dose level. However, given the fact that a 1.5-fold increase in TMZ and a 10-fold increase in MX is being tested in 7 dose escalation levels it is highly unlikely that the maximum number of patients will need to be enrolled at each level.

The following table gives the probabilities of escalating under given true but unknown underlying rates of DLT:

True Underlying DLT Rate	0.1	0.2	0.3	0.4	0.5
Escalate to next full dose	0.91	0.71	0.49	0.32	0.17
Do not escalate; prior dose level is MTD	0.09	0.29	0.51	0.68	0.83

Thus, if the true underlying rate of DLT is 20%, there will be a 71% chance of escalating to next full dose and a 29% chance that the lower dose will be chosen as the MTD.

The baseline levels (at 0h) of AP sites and DNA strand breaks will be compared to the levels at various time points (i.e. 2h, 4h and 122h) after treatment by paired T-test or Wilcoxon rank sum test. The predictive value of PK parameters (e.g. AUC, C_{max}), levels of AP sites and levels of DNA strand breaks on clinical response and grade 3/4 toxicity will be examined by logistic regression after adjusting the dose level; their predictive value on time to event outcomes, such as disease progression free survival, will be tested using (extended) Cox model after controlling other factors including dose level.

REFERENCES

1. L Liu, P Taverna, CM Whitacre, S Chatterjee, and SL Gerson. Pharmacologic disruption of base excision repair sensitizes mismatch repair-deficient and -proficient colon cancer cells to methylating agents. *Clin Cancer Res* 5:2908-2917, 1999.
2. L Liu, Y Nakatsuru, and SL Gerson. Base excision repair as a therapeutic target in colon cancer. *Clin Cancer Res* 8:2985-2991, 2002.
3. L Liu, JR Donze, and SL Gerson. Methoxyamine enhances antitumor efficacy of BCNU in colon tumor xenografts. *Proc Amer Assoc Cancer Res* 43:794 (#3938), 2002.

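### Study Calendar footnote i requires a Cohort B screening MMSE below 15, but exclusion 3.2.6 bars Cohort B patients who score below 15, so no patient can meet both

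*Combined protocol and SAP*

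**What the plan says.** Two current passages set an MMSE threshold for Cohort B, the patients with primary or metastatic CNS disease.

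- **Section 3.2.6 (exclusion):** "Patients with known primary or metastatic CNS disease (cohort B) are not eligible if they have a" score below 15 on the Appendix D form. Leptomeningeal disease is a separate ground for exclusion in the same item.
- **Section 8, footnote i:** "MMSE to be done at screening for subjects in Cohort B only", followed by "These subjects must have a score of < 15. See appendix D".

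The calendar marks the MMSE once, in the pre-study column, so screening is its only scheduled use. Both texts refer to Appendix D. That appendix contains the questionnaire and a total out of 30, with no eligibility cut-off.

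**The concern.** The two texts use the same number and the same inequality sign with opposite effect. A coordinator working from the calendar and one working from Section 3.2 would reach opposite decisions on every Cohort B candidate.

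The cohort makes this more than an editorial matter. Section 2 records that neurotoxicity was dose-limiting in animal studies of the combination, and that the FDA advised keeping patients with brain metastasis or glioma out of the initial study. Under Section 4.2 a toxicity counts as a DLT only if it is one "that is felt to be related to MX or the MX + TMZ drug combination occurring during the first cycle of treatment". If the footnote were followed, Cohort B would consist of patients with low baseline cognitive scores, and it would be harder to judge whether a new neurologic event was caused by the drug. The v22 provision adds to this: after one DLT in three patients at Cohort B level 6, whether escalation continues depends on whether that DLT was of CNS type.

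The protocol does not state the purpose of the MMSE cut-off, so the link to DLT attribution is an inference.

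**Working it through.** No sample-size or power formula applies. The check lists the scores that each text allows.

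**Range of the instrument (Appendix D).** The item maxima, in order, are orientation 5 + 5, registration 3, attention 5, recall 3, naming 2, repetition 1, three-stage command 3, reading 1, writing 1, copying 1.

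5 + 5 + 3 + 5 + 3 + 2 + 1 + 3 + 1 + 1 + 1 = 30

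This matches the printed total. Possible scores are the integers 0 to 30, which is 31 values.

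**Scores each text allows in Cohort B**

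| Text | Rule | Scores allowed | Count |
|---|---|---|---|
| Section 8, footnote i | must be < 15 | 0-14 | 15 |
| Section 3.2.6 | ineligible if < 15 | 15-30 | 16 |
| Both | | none | 0 |

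15 + 16 = 31, so the two sets divide the whole scale with no overlap.

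**Could a lost underline (≤ read as <) explain it?**

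- Both signs ≤: the footnote allows 0-15 and 3.2.6 leaves 16-30. No overlap.
- Only 3.2.6 ≤: the footnote allows 0-14 and 3.2.6 leaves 16-30. No overlap.
- Only the footnote ≤: the footnote allows 0-15 and 3.2.6 leaves 15-30. The single score 15 meets both.

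No such reading gives a workable rule.

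**Does another part of the protocol settle it?**

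- Appendix D has no cut-off.
- Section 3.2.7 allows an exception. Cohort B patients with neurologic toxicity above grade 2 "are not eligible, unless pre-existing neurotoxicity is documented in detail" and the neuro-oncology team approves. That concerns CTCAE grade, not the MMSE score.
- Section 4 requires a "copy of the signed eligibility criteria from the study protocol" at registration. This points staff to Section 3, but it does not say that Section 3 overrides the calendar.
- The text available for review contains no clause saying which section prevails.

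**Number of records.** Section 12 states: "For cohort B, a maximum of 42 patients can theoretically participate on this study". That is 7 dose levels × 6 patients = 42. It indicates how many enrolment records the conflicting wording could cover. It does not count patients wrongly enrolled.

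**The case against.** The strongest reply is that this is a slip in a scheduling table that nobody would act on. Eligibility is read from Section 3, and the signed criteria must be filed before treatment. Criterion 3.1.9 separately requires the ability to understand the consent document, and a neurologist sees every patient before treatment starts. Enrolling only patients who score 0-14 would mean overriding 3.2.6 with all of these checks in place. A query to the coordinator is the more likely result.

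Section 3 also explains that Cohort A exists so that CNS toxicity can be judged without confounding from existing disease. Some confounding in Cohort B is therefore accepted by design, and Section 4.2 provides specialist consults when neurologic toxicity worsens.

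Most of this stands as an argument about likelihood. It makes systematic misenrolment improbable and keeps the DLT argument conditional. It does not make the two texts agree: the footnote is worded as a requirement, and a monitor auditing against the protocol has no single rule to apply.

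Two further points are fair. Section 12 itself calls enrolment of the maximum number at each level highly unlikely. Nor has six per level been a firm cap elsewhere: Cohort A level 1 was expanded to 10 evaluable patients and Cohort A level 7 treated seven. So 42 is a planning figure, not a bound on the records to check. Also, a check confined to enrolled patients would miss anyone turned away because the footnote had been applied.

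**Conclusion.** The contradiction holds as written. For the same cohort, instrument and time point, one current passage requires a score below 15 and another excludes it. None of the 31 possible scores meets both, so every Cohort B enrolment departs from one of them.

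The practical effect is limited. No misenrolment is shown, the registration procedure favours Section 3, and sample size, the escalation table and the planned analyses do not change. Any effect on DLT attribution assumes that the footnote was actually used at screening, which the documents do not indicate.

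It should be fixed, because it reverses an eligibility threshold in an operative instruction for the cohort with CNS disease. The footnote may be a reversed sign or a dropped negation, but the documents do not say so, and this review takes no position on which threshold is right.

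**What to change.** 1. The sponsor should reconcile Section 3.2.6 with footnote i of Section 8 and confirm the intended rule.
2. State the cut-off once, in Section 3.2, and reduce footnote i to timing, cohort and a cross-reference, for example: MMSE at screening, Cohort B only; see 3.2.6.
3. Check the screening MMSE of every enrolled Cohort B patient against the reconciled rule and list any deviations. Include Cohort B screen failures, so that patients wrongly turned away are also found.

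The cost is one footnote in the next amendment and a short record check: up to 42 enrolled patients on Section 12's planning figure, plus the screen failures, whose number the documents do not give. Sample size, escalation rules and analyses need no change.

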9. MEASUREMENT OF EFFECT

Although response is not the primary endpoint of this trial, patients with measurable disease will be assessed by standard criteria. For the purposes of this study, patients should be reevaluated every 8 weeks. For measurement of effect purposes, baseline imaging studies are the ones obtained pretreatment. If a patient has a complete response, partial response or stable disease, a confirmatory scans will be obtained at least 4 weeks following initial documentation of an objective response. Imaging evaluations will then return to an every 8 week schedule. All responses will be reviewed by the Cancer Center Data Safety and Toxicity Committee.

9.1 Definitions

Response and progression will be evaluated in this study using the new international criteria proposed by the Response Evaluation Criteria in Solid Tumors (RECIST) Committee [JNCI 92(3):205-216, 2000]. Changes in only the largest diameter (unidimensional measurement) of the tumor lesions are used in the RECIST criteria. Note: Lesions are either measurable or non-measurable using the criteria provided below. The term “evaluable” in reference to measurability will not be used because it does not provide additional meaning or accuracy.

9.1.1 Measurable Disease

Measurable lesions are defined as those that can be accurately measured in at least one dimension (longest diameter to be recorded) as ≥ 20 mm with conventional techniques (CT, MRI, x-ray) or as ≥ 10 mm with spiral CT scan. All tumor measurements must be recorded in millimeters (or decimal fractions of centimeters).

9.1.2 Non-measurable Disease

All other lesions (or sites of disease), including small lesions (longest

diameter <20 mm with conventional techniques or <10 mm using spiral CT scan), are considered non-measurable disease. Bone lesions, leptomeningeal disease, ascites, pleural/pericardial effusions, lymphangitis cutis/pulmonis, inflammatory breast disease, abdominal masses (not followed by CT or MRI), and cystic lesions are all non-measurable.

9.1.3 Target Lesions

All measurable lesions up to a maximum of five lesions per organ and 10 lesions in total, representative of all involved organs, should be identified as **target lesions** and recorded and measured at baseline. Target lesions should be selected on the basis of their size (lesions with the longest diameter) and their suitability for accurate repeated measurements (either by imaging techniques or clinically). A sum of the longest diameter (LD) for all target lesions will be calculated and reported as the baseline sum LD. The baseline sum LD will be used as reference by which to characterize the objective tumor response.

9.1.4 Non-target Lesions

All other lesions (or sites of disease) should be identified as **non-target lesions** and should also be recorded at baseline. Non-target lesions include measurable lesions that exceed the maximum numbers per organ or total of all involved organs as well as non-measurable lesions. Measurements of these lesions are not required but the presence or absence of each should be noted throughout follow-up.

